1.2 Secondary Objectives

- Estimate the 6-month and median progression free survival (PFS) rates
- Estimate the 2-year and median overall survival (OS) rates
- Evaluate the safety of trametinib in patients with epithelioid hemangioendothelioma
- Evaluate patient-reported symptoms using NIH PROMIS global health; pain intensity, interference and behavior short form inventories prior to, after 4 weeks and after 6 months (if stable or better disease) of treatment, and on evidence of disease progression

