- e: Tumor digital files to be sent to QARC for tumor volume assessment.
- f: Tumor measurements do not need to be repeated if patient ends treatment because of documented tumor progression by imaging.
- g: Blood or urine pregnancy test (women of childbearing potential).
- h: NIH PROMIS global health, pain intensity, interference and behavior short form inventories to be obtained prior to trametinib treatment, after 1 month and 6 months of treatment, and on evidence of disease progression or response.
- i: For patients remaining on treatment after week 12, evaluations will include physical exam, weight, performance status, complete blood count with differential and platelet count, and serum chemistry at least once per cycle.

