11. MEASUREMENT OF EFFECT

11.1 Antitumor Effect – Solid Tumors

For the purposes of this study, patients should be re-evaluated for response every 8 weeks (\pm 7 days) for the first 24 weeks, then every 12 weeks (\pm 7 days). In addition to a baseline scan, confirmatory scans should also be obtained 4 to 8 weeks following initial documentation of objective response.

Response and progression will be evaluated in this study using the new international criteria proposed by the revised Response Evaluation Criteria in Solid Tumors (RECIST 1.1) guideline (version 1.1) [Eur J Ca 45:228-247, 2009]. Changes in the largest diameter (unidimensional measurement) of the tumor lesions and the shortest diameter in the case of malignant lymph nodes are used in the RECIST 1.1 criteria.

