Secondary objectives of the 6-month PFS rate, median PFS, and 2-year OS rate will be determined from analyses of patients with *TAZ-CAMTA1* translocation positive EHE. Evaluation of the safety of trametinib, and patient reported symptoms using NIH-PROMIS questionnaires will be determined from analyses of all patients who started treatment with trametinib.

Progression-free survival will be calculated from time of first dose of study medication to occurrence of radiologic tumor progression per RECIST1.1, clinical progression based on treating physician's assessment or death from any cause. Overall survival will be calculated from the time of first dose of study drug to occurrence of death from any cause. Patients who are registered and are determined to be eligible for study treatment but do not start study drug will be replaced. All patients who receive study drug for any period of time will be evaluable for toxicity. The rates of adverse events occurring in at least 5% of subjects and rates of grade 3-5 adverse events will be tabulated by system and term using Common Terminology Criteria of Adverse Events (CTCAE). For dose adjustment schedule see Section 6.1. PROMIS questionnaires will be scored according to recommended standardized system and t-scores generated. A mixed model will be used to analyze change in t-scores over time. Whether or not having evidence of disease progression will be used as a time-dependent variable in the mixed model with adjustment of other potential confounding variables.

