13.2 Sample Size/Accrual Rate

This study will be conducted in a two-stage process. In stage I, 13 patients with EHE will be enrolled. If there is at least 1 objective response, additional patients will be enrolled in stage II until there is evidence that a total of 27 patients with EHE with *TAZ-CAMTA1* translocation detected by fusion FISH have been registered and started treatment. After 27 patients have been enrolled and started treatment, enrollment of additional patients will be held until FISH testing is performed on available tissue from the enrolled patients. One enrollment slot will be opened for each case of FISH result of *TAZ-CAMTA1* translocation "not detected", "test failed", or "test not performed" (no tumor tissue in sample) until a total of 27 patients have enrolled and started treatment with FISH result of *TAZ-CAMTA1* translocation "detected". Enrollment in the second stage will be held until at least 1 objective response has occurred. Enrollment for stage I is anticipated to be complete within the first 12 months of study activation. Enrollment for stage II is anticipated to be complete within 18 months of proceeding to stage II. We anticipate that on average, 1 patient per month will be accrued to the study. The study is open to all eligible persons at least 15 years of age. Because of the very rare nature of the disease under study, we will not restrict enrollment based on sex, race or ethnicity in order to complete accrual within 2-3 years.

PLANNED ENROLLMENT REPORT

Racial Categories	Ethnic Categories				Total
	Not Hispanic or Latino		Hispanic or Latino		
	Female	Male	Female	Male	
American Indian/ Alaska Native	0	0	0	0	0
Asian	1	1	0	0	2
Native Hawaiian or Other Pacific Islander	0	0	0	0	0
Black or African American	3	2	0	0	5
White	9	6	2	1	18
More Than One Race	1	1	0	0	2
Total	14	10	2	1	27

PHS 398 / PHS 2590 (Rev. 08/12 Approved Through 8/31/2015)

OMB No. 0925-0001/0002

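### The only PROMIS model adjusts for progression, so its time effect describes patients who have not progressed, not all treated patients

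*Combined protocol and SAP*

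**What the plan says.** Section 13.1 sets the population for this secondary objective: "patient reported symptoms using NIH-PROMIS questionnaires will be determined from analyses of all patients who started treatment with trametinib". The analysis follows: "A mixed model will be used to analyze change in t-scores over time". The next sentence specifies the covariates: "Whether or not having evidence of disease progression will be used as a time-dependent variable in the mixed model", together "with adjustment of other potential confounding variables", which are not named. The plan gives no PROMIS hypothesis, significance level, time coding, interaction, reported contrast or averaging over progression status, and no other section adds a PROMIS analysis.

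The collection schedule appears twice. After the baseline form, Section 1.2 asks for forms "after 4 weeks and after 6 months (if stable or better disease) of treatment, and on evidence of disease progression". Section 10, footnote h, asks for them "after 1 month and 6 months of treatment, and on evidence of disease progression or response". The footnote does not limit the 6-month form to patients with stable or better disease, and it adds a form at response.

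**The concern.** By naming other confounders alongside it, the plan treats progression as a confounder. It cannot confound change from baseline: it arises after treatment starts, and it is one route by which failing treatment makes symptoms worse. Adjusting for it moves the worsening at progression out of the time effect and into the progression term.

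With a single arm, no control comparison would expose this. A reader of the results would naturally take the time effect as the symptom change on trametinib in everyone treated. If symptoms differ by progression status, that reading is wrong, and the plan offers no other estimate.

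**Working it through.** **Plan's own figures.** There are none for PROMIS. The only operating characteristics in Section 13 concern the response rate (5% type I error, about 80% power, 51% early stopping). They reproduce at 4.2%, 80.1% and 51.3% and have no bearing here.

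**Inputs from the documents.**
- Treated patients: 27 fusion-positive (Section 13.2: "a total of 27 patients have enrolled and started treatment with FISH result") plus the stage I cases in Section 13.1 with no fusion detected (3) or too little tissue (1). This gives 27 + 3 + 1 = 31, used as the working N.
- Share progressed at 6 months (pi): not stated for this trial. The sorafenib study in Section 2.1 had 38.4% progression-free, so pi = 1 - 0.384 = 0.616. Values of 0.50 and 0.30 are also tried.
- Scan times: Section 11.1 ("patients should be re-evaluated for response every 8 weeks" in the first 24 weeks), simulated as months 2, 4 and 6.

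T-score SDs, correlations and score changes are assumptions. Negative values mean less pain.

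**Step 1: algebra.** Write the model as y = b0 + f(t) + g*P(t) + patient effect + error, where P(t) = 1 once the patient has progressed on study. Everyone has P = 0 at baseline. Let d0 and d1 be the changes in unprogressed and progressed patients. Then f = d0 and g = d1 - d0, and the all-treated change is (1 - pi)*d0 + pi*d1 = f + g*pi. The time effect f equals this only when g*pi = 0.

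**Step 2: unprogressed patients flat.** With d0 = 0, d1 = +5 and pi = 0.616, the all-treated change is 0.616 x 5 = +3.1. In simulation (N = 31, SD 9, correlation 0.6) the time effect is about 0 with the term and about +3 without it. In the flat scenarios, the unadjusted model detected the net worsening in 41-53% of runs.

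**Step 3: zero all-treated change.** This requires d0 = -pi*d1/(1 - pi).
- pi = 0.50: d1 = 2 to 5 gives d0 = -2 to -5.
- pi = 0.616: the ratio is 0.616/0.384 = 1.604, so d1 = 2 to 5 gives d0 = -3.2 to -8.0.

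With the same SD and correlation, and time coded by visit, a significant improvement (two-sided 5%, so 2.5% in that direction) appears in 16-95% of runs with the term and 2-5% without it.

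**Step 4: a second set of assumptions.** Between-patient SD 7, within-patient SD 5, 600 runs per setting, Section 1.2 schedule, visit-coded time, all-treated change zero:

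| pi | d0 | d1 | With term: mean; significant improvement | Without term: mean; significant improvement |
|---|---|---|---|---|
| 0.30 | -3 | +7.0 | -3.1; 58% | -0.03; 3.8% |
| 0.50 | -3 | +3.0 | -2.9; 43% | +0.06; 2.5% |
| 0.616 | -3 | +1.87 | -3.0; 37% | 0.00; 2.2% |
| 0.30 | -5 | +11.67 | -5.0; 93% | -0.04; 4.2% |
| 0.50 | -5 | +5.0 | -5.0; 84% | +0.07; 4.0% |
| 0.616 | -5 | +3.12 | -5.0; 78% | -0.03; 2.3% |

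Scoring every patient at month 6 whatever their status gives nearly the same picture: 37-56% (d0 = -3) and 75-93% (d0 = -5) with the term, 2.5-4.7% without. The cause is therefore the covariate and not missing visits.

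**Step 5: nobody changes.** Significant improvement appears in 1.7-3.0% of runs with the term and 2.2-3.2% without, both near 2.5%.

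**Step 6: time coding.** Under the Section 1.2 schedule, dropping the term but treating time as linear still leaves an apparent improvement at zero net change: 0.4-1.6 points (5-16% significant) under the Step 3 assumptions and 0.9-2.0 points (7-25%) under those of Step 4. Progressors are scored earlier and have no month-6 form. If visits are instead coded as baseline, week 4, month 6 and progression, the progression term duplicates the progression visit (rank 4 with 5 columns) and the two effects cannot be separated.

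**The case against.** The progression contrast may be intended. Forms are timed to disease status, and a time-dependent term suits the question of how symptoms differ at progression. The sentence about all treated patients sets the analysis population, in contrast to the fusion-positive set used for PFS and OS; it does not name an estimand. The all-treated change could also be recovered as f + g*pi. These points explain why the term is there and justify keeping that model, but the plan does not call for the recovery step.

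A reader might infer that the model inflates type I error or is biased toward benefit. The documents do not support that. Section 13.1 states no PROMIS null or test, rates stay near nominal when nobody changes, and the model shows improvement only when unprogressed patients truly improve. In the Step 3 scenarios that improvement is 2 to 8 points, the upper end being about 0.9 SD (8/9). The significant results there are correct for unprogressed patients and wrong only if read as applying to everyone treated.

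It is also fair that the time coding, SDs and size of worsening are assumed, and that if scores do not differ by progression status there is no distortion.

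**Conclusion.** The point holds as a mismatch between the stated analysis (change over time in all treated patients) and what the planned time effect estimates (change while unprogressed). This follows from the specification and needs no simulation. The mismatch equals g*pi: about 3 points of hidden worsening in the flat example, and 2 to 8 points of improvement reported against a true zero in the Step 3 scenarios. Those sizes rest on 31 patients, the assumed SDs and correlations, and 50-61.6% progressed by 6 months.

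It should be corrected, but the stakes are limited. PROMIS is one secondary objective, activity is judged on the response rate alone, and a single-arm time trend is not a causal estimate under either model.

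**What to change.** In Section 13.1:

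1. For the secondary objective, report change from a mixed model without progression status, adjusting for named baseline covariates only and using all forms from all treated patients, including those completed at progression.
2. Code time by visit category (baseline, week 4, last assessment = month 6 or progression), not linearly. State that the final contrast is the change to whichever of the two applies, and say where forms completed at response or at progression after month 6 enter the model.
3. Keep the progression-adjusted model as a separately labelled analysis of how symptoms differ at progression, and state that its time effect applies only to unprogressed patients.
4. Reconcile Section 1.2 with Section 10, footnote h, on whether the 6-month form is limited to patients with stable or better disease, and on the form at response.

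The cost is a few sentences and one extra model on forms already scheduled. The symptom estimate may be less favourable. Precision need not suffer: under the Step 4 assumptions with half progressed and everyone improving 3 points, the model without the term found a significant improvement in 63% of runs, against 42% with it.

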13.2 Sample Size/Accrual Rate

This study will be conducted in a two-stage process. In stage I, 13 patients with EHE will be enrolled. If there is at least 1 objective response, additional patients will be enrolled in stage II until there is evidence that a total of 27 patients with EHE with *TAZ-CAMTA1* translocation detected by fusion FISH have been registered and started treatment. After 27 patients have been enrolled and started treatment, enrollment of additional patients will be held until FISH testing is performed on available tissue from the enrolled patients. One enrollment slot will be opened for each case of FISH result of *TAZ-CAMTA1* translocation "not detected", "test failed", or "test not performed" (no tumor tissue in sample) until a total of 27 patients have enrolled and started treatment with FISH result of *TAZ-CAMTA1* translocation "detected". Enrollment in the second stage will be held until at least 1 objective response has occurred. Enrollment for stage I is anticipated to be complete within the first 12 months of study activation. Enrollment for stage II is anticipated to be complete within 18 months of proceeding to stage II. We anticipate that on average, 1 patient per month will be accrued to the study. The study is open to all eligible persons at least 15 years of age. Because of the very rare nature of the disease under study, we will not restrict enrollment based on sex, race or ethnicity in order to complete accrual within 2-3 years.

PLANNED ENROLLMENT REPORT

Racial Categories	Ethnic Categories				Total
	Not Hispanic or Latino		Hispanic or Latino		
	Female	Male	Female	Male	
American Indian/ Alaska Native	0	0	0	0	0
Asian	1	1	0	0	2
Native Hawaiian or Other Pacific Islander	0	0	0	0	0
Black or African American	3	2	0	0	5
White	9	6	2	1	18
More Than One Race	1	1	0	0	2
Total	14	10	2	1	27

PHS 398 / PHS 2590 (Rev. 08/12 Approved Through 8/31/2015)

OMB No. 0925-0001/0002

13.3 Stratification Factors

None.

13.4 Analysis of Exploratory Endpoints

Exploratory correlative studies will evaluate rates of EHE growth prior to starting trametinib to growth rates on treatment, the change in c-reactive protein (CRP), erythrocyte sedimentation rate (ESR), plasma connective tissue growth factor (CTGF) and tumor volume as potential biomarkers of EHE activity, and the effect of trametinib on MAP kinase activation.

Digital files of cross-sectional radiology images (CT and MRI) will be provided to [name] (Columbia University, NY) to evaluate the change in rate of EHE growth pre-trametinib therapy and on trametinib. Evidence of tumor progression per RECIST will be required for enrollment of patients (except in setting of severe tumor-related pain); therefore, longitudinal pre-treatment radiology images will be available in the majority of cases for comparison. A 50% or more reduction in the change in tumor size/unit of time following start of treatment with trametinib will be considered clinically significant. McNemar test will be used to compare the number of patients with EHE progression prior to starting trametinib to the number

of patients with EHE progression during treatment.

Patient CTGF samples collected at indicated time points will be run in triplicate and average values used for the comparison. The CTGF, CRP and ESR levels over time will be used as time-dependent variables in a Cox model to determine the association with EHE survival.

The agreement of change in tumor volume and in tumor size assessed by RECIST will be summarized with a scatterplot. The Pearson correlation coefficient (or Spearman, if more appropriate) will be assessed to determine the strength of the agreement. Agreement of the tumor classifications (response versus no response) will be summarized as the raw agreement and with a Kappa Statistic. The association of the change in tumor volume with survival will be evaluated in two ways. The first will be to use the change in tumor volume as a time dependent variable in a Cox model. The second will be a landmark analysis (done at either the first radiographic assessment or at the second radiographic assessment) to compare the survival of patients classified as a responder (based on tumor volume) to those who have not responded by the selected landmark time. Patients who died prior to the landmark time point will be omitted from analysis.

Evaluation of MAP kinase activation is an exploratory analysis on relatively few samples. In another multicenter SARC phase II clinical trial (SARC028) that required paired pre-treatment and on-treatment tumor biopsy, matched samples were obtained in 75% of the cases and tumor biopsy was performed in about 50% of patients at the time of progression. We estimate a similar success rate in obtaining matched tumor tissue. Descriptive statistics will be generated, and estimates for the proportion of samples with demonstrated inhibition of MAPK signaling post-treatment compared to pre-treatment will be generated along with 95% confidence intervals. Likewise, the proportion of patients with demonstrated MAPK signaling inhibition at time of disease progression will be determined with the corresponding 95% confidence interval. These are exploratory analyses and all available data will be used.

Evaluation of presence of *TAZ-CAMTA1* gene fusion will be performed by FISH. Tumor in which at least 10% of nuclei are scored as having a fused signal will be counted as EHE with presence of *TAZ-CAMTA1* translocation. The number and percent of *TAZ-CAMTA1* gene fusion positive EHE will be reported.

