3. PATIENT SELECTION

3.1 Eligibility Criteria

- 3.1.1 Patients must have measurable disease, defined as at least one lesion that can be accurately measured in at least one dimension (longest diameter to be recorded for non-nodal lesions and short axis for nodal lesions) as ≥ 20 mm (≥ 2 cm) with conventional techniques or as ≥ 10 mm (≥ 1 cm) with spiral CT scan, MRI, or calipers by clinical exam. Baseline imaging must be obtained within 30 days of Day 1 of study. See Section 11 for the evaluation of measurable disease.
- 3.1.2 Patients must have histologically confirmed epithelioid hemangioendothelioma which is metastatic or locally advanced (unresectable), and tumor tissue (paraffin-embedded tissue block or tumor tissue on unstained glass slides) available for fusion FISH analysis at Cleveland Clinic. Patient tumor tissue stored in pathology archives may be used for fusion FISH; a new biopsy is not mandatory.

- 3.1.3 Patients must have evidence of disease progression per RECIST1.1 prior to enrollment or have evidence of cancer-related pain requiring symptom management with narcotic analgesics.
- 3.1.4 Because there is no established standard or approved drug therapy for treatment of EHE, patients previously untreated or treated with drug therapy for EHE are eligible. There is no limit on the number of prior regimens used to be eligible.
- 3.1.5 Age ≥ 15 years. EHE is very unlikely to arise before the age of 15 years.
- 3.1.6 ECOG performance status ≤ 2 (Karnofsky $\geq 60\%$, see Appendix A).
- 3.1.7 Life expectancy of greater than 6 months.
- 3.1.8 Able to swallow orally-administered medication and does not have any clinically significant gastrointestinal abnormalities that may alter absorption such as malabsorption syndrome or major resection of the stomach or small bowel.
- 3.1.9 All prior treatment-related toxicities must be CTCAE v5 grade ≤ 1 (**except alopecia**) at the time of enrollment.
- 3.1.10 Patients must have normal organ and marrow function as defined below within 2 weeks of patient registration (for blood results) and 30 days of registration for LVEF assessment:
 - Absolute neutrophil count (ANC) $\geq 1 \times 10^9/L$
 - Hemoglobin ≥ 9 g/dL, patients may receive transfusion to meet criterion
 - Platelets $\geq 75 \times 10^9/L$
 - Albumin ≥ 2.5 g/dL

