9.4.1.2 Assessment

9.4.1.2.1. Sites of tumor will be imaged by CT or MRI using standard protocols.

9.4.1.2.2. Imaging tumor will occur within 30 days prior to starting drug, after cycles 2, 4 and 6 and thereafter approximately every 12 weeks. For patients with evidence of disease progression prior to enrollment, CT or MRI scans documenting progression will also be reviewed.

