11.1.4 Response Criteria

11.1.4.1 Evaluation of Target Lesions

Complete Response (CR): Disappearance of all target lesions. Any pathological lymph nodes (whether target or non-target) must have reduction in short axis to <10 mm (<1 cm).

Partial Response (PR): At least a 30% decrease in the sum of the diameters of target lesions, taking as reference the baseline sum diameters.

Progressive Disease (PD): At least a 20% increase in the sum of the diameters of target lesions, taking as reference the smallest sum on study (this includes the baseline sum if that is the smallest on study). In addition to the relative increase of 20%, the sum must also demonstrate an absolute increase of at least 5 mm (0.5 cm). (Note: the appearance of one or more new lesions is also considered progressions).

Stable Disease (SD): Neither sufficient shrinkage to qualify for PR nor sufficient increase to qualify for PD, taking as reference the smallest sum diameters while on study.

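### The 50% growth-slowing rule in section 13.4 fixes no scans and has no confirmation or error allowance, so noise and selection can meet it without any drug effect

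*Combined protocol and SAP*

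**What the plan says.** Section 1.3 lists, as the first exploratory objective, a centrally read comparison of progression rates before and on trametinib. Section 13.4 then sets a per-patient threshold: "A 50% or more reduction in the change in tumor size/unit of time following start of treatment with trametinib will be considered clinically significant". This is separate from the McNemar test in the same paragraph.

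The pre-treatment rate is tied to how patients enter. Eligibility criterion 3.1.3 reads: "Patients must have evidence of disease progression per RECIST1.1 prior to enrollment or have evidence of cancer-related pain requiring symptom management with narcotic analgesics". Section 13.4 relies on this to say that "longitudinal pre-treatment radiology images will be available in the majority of cases for comparison". Section 9.4.1.2 adds: "For patients with evidence of disease progression prior to enrollment, CT or MRI scans documenting progression will also be reviewed".

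Target-lesion progression in section 11.1.4.1 means "At least a 20% increase in the sum of the diameters of target lesions, taking as reference the smallest sum on study", with an absolute increase of at least 5 mm. The same section notes that "the appearance of one or more new lesions is also considered progressions", and section 11.1.4.2 allows progression in non-target lesions.

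Baseline imaging must fall within 30 days of Day 1 (3.1.1). On-treatment imaging is every 8 weeks to week 24, then every 12 weeks (11.1). Confirmation is written for objective response only (11.1, 11.1.4.3).

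**The concern.** Section 13.4 leaves open which pre-treatment interval sets the reference rate, which on-treatment scan counts, and whether the scan that showed progression may also be the baseline. It gives no expected proportion for an inactive drug.

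For a patient who qualified by target-lesion growth, two mechanisms favour the rule:

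- **Selection.** Entry required a high measured increase, so true growth is on average lower than the measured pre-treatment rate.
- **Shared error.** If the qualifying scan is also the baseline, an over-reading raises the pre-treatment rate and lowers the on-treatment rate.

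Without a control arm, a count of patients with clinically significant slowing has nothing to be compared with. A reader could take as drug activity what measurement error alone would produce.

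**Working it through.** **1. The plan's own figures.** The only operating characteristics stated are those of the two-stage design (13.1), and they reproduce. The chance of stopping after stage I at a 5% response rate is 0.95^13 = 0.513 (stated 51%). Summing P(X1 = x) × P(X2 ≥ 4 − x) over x = 1 to 13, with X1 from 13 patients and X2 from 14, gives power 0.801 at 20% (stated about 80%) and type 1 error 0.042 at 5% (within the stated 5%). No such figure exists for the growth-rate rule.

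**2. Noise alone, by hand.** Assume a sum of 60 mm, true growth of 20% over 12 weeks (1 mm/week), no drug effect, and 5% error on each reading. True sums are m0 = 60, m1 = 72 (also the baseline), and 80 at week 8; error SDs are 3, 3.6 and 4 mm.

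- Rule at week 8: (m2 − m1)/8 ≤ 0.5 × (m1 − m0)/12, that is D = m2/8 − m1/6 + m0/24 ≤ 0.
- Mean of D = 10 − 12 + 2.5 = 0.5. SD = √[(4/8)² + (3.6/6)² + (3/24)²] = √0.6256 = 0.791.
- P(D ≤ 0) = Φ(−0.5/0.791) = Φ(−0.632) = 0.26.
- Read at week 24 (true sum 96 mm, SD 4.8): D = m2/24 − m1/12 + m0/24, mean 0.5, SD = √(0.2² + 0.3² + 0.125²) = 0.382. P = Φ(−1.310) = 0.095.

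With no measurement error and constant linear growth, the proportion is 0.

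**3. Adding selection.** In the same setting (linear growth, 5% error, 3-month interval, shared scan, week 8), I simulated the proportion with and without conditioning on a measured increase of at least 20%:

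| True growth over the interval | Selected | Not selected |
|---|---|---|
| 15% | 63% | 31% |
| 20% | 44% | 26% |
| 25% | 30% | 23% |
| 30% | 22% | 19% |

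Noise over a short interval is a large part of the effect. Selection adds most when true growth is at or below the 20% threshold.

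**4. Simulation with varied growth.** Assumptions, none from the documents: 60 mm starting sum; pre-treatment scans every 12 weeks; constant log-growth per patient with mean 0.05, 0.10 or 0.20 per 12 weeks, with spread between patients (SD 0.05, 0.08, 0.10) or, for the faster means, none. From the documents: entry at the first increase of at least 20% and 5 mm over nadir. No drug effect. The separate baseline is a scan 4 weeks after the qualifying one.

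| Error (CV) | Read at | Qualifying scan is baseline | Separate baseline |
|---|---|---|---|
| 5% | Week 8 | about 22–56% | about 15–39% |
| 5% | Week 24 | about 1–38% | about 0–25% |
| 3% | Week 8 | about 7–34% | about 4–23% |
| 8% | Week 8 | about 36–71% | about 27–51% |

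Mean growth of 5% with no spread between patients lies outside these ranges: about 69% at week 8 with a shared scan and 5% error. A linear-growth model at 5% error, with true growth of 20–30% over 2–6 months, gives 14–55% (shared) and 12–40% (separate). Across errors of 2–10%, intervals of 2–12 months and growth of 20–50%, the range is about 0–65%.

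**5. The remedy in the same simulation** (5% error, separate baseline, spread between patients):

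| Method | No effect, scored | True 70% reduction, scored |
|---|---|---|
| Two scans, week 8 | about 16–39% | about 60% |
| Two scans, week 24 | about 4–25% | about 70–73% |
| Log-size slopes through week 24 | about 5–25% | about 70–87% |

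The lower false-positive rate comes mainly from longer follow-up and the separate baseline. Regression itself adds mostly detection.

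**The case against.** A reader might infer that an inactive drug would make 15–55% of the whole cohort, or about 4–15 of 27 patients, clinically significant at the first scan. The documents do not support that:

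- **Timing.** Section 13.4 refers only to the period after treatment starts. Week 8 is the noisiest permissible reading; week 24 gives far less.
- **Who is affected.** Entry on narcotic-requiring pain, new lesions or non-target progression involves no selection on 20% growth, and 3.1.3 sets no time window, so the growth need not be recent. Scaling to all 27 is unsupported.
- **Inputs.** Measurement error, growth rate and pre-treatment interval are all assumed.
- **Readers.** Section 3.1.3 does not say that entry progression is read centrally, whereas the growth rates are. With fully independent central error at 5%, the week-8 range falls to 17–35% (shared) and 14–33% (separate).
- **Natural history.** Section 2.1 describes long stability followed by rapid progression. Acceleration would lower the no-effect proportion; I did not simulate it.
- **Consequence.** The analysis is exploratory, with no success threshold on the proportion. The activity decision rests on four RECIST responses in 27 (13.1).

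All of this stands and limits the size. It does not remove the problem: even with independent central reads, or at week 24, the proportion remains material in many scenarios. Without any selection, at 5% error and a shared scan, 20–47% of patients with a positive measured pre-treatment rate still meet the rule at week 8. For a zero or negative pre-treatment rate, a percentage reduction has no sensible meaning, and section 13.4 gives no rule.

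**Conclusion.** The point holds in a limited form. The section 13.4 rule attaches a claim of clinical significance to a threshold that noise and regression to the mean can meet with no drug effect, most clearly in patients who entered by target-lesion growth. Under the stated assumptions at 5% error, the no-effect proportion is about 15–55% at week 8 and about 0–38% at week 24. These figures are conditional on inputs that the documents lack, and should be presented as a range over assumptions rather than as a property of the trial. The primary endpoint and the go/no-go decision are unaffected. The change is worth making because it is cheap and the rule serves the first exploratory objective.

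**What to change.** Reword the rule in section 13.4:

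- Estimate pre-treatment and on-treatment slopes by regression of log tumor size on actual scan date, using all available centrally read scans, on treatment through week 24.
- Where a separate pre-treatment baseline scan exists, start the on-treatment slope there and not at the progression scan.
- Score a reduction of at least 50% only with two or more on-treatment scans and a positive pre-treatment slope.
- Report the mean slope change with a 95% CI, and show the observed proportion beside a no-effect proportion simulated over a stated range of measurement error.

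The cost is SAP wording and modest analysis work. Some patients cannot be scored, and the reported proportion will be less favourable. Sections 9.4.1.2 and 11.1.7 clearly request only the baseline scan and the scans documenting progression, so earlier scans may be missing. Where only the qualifying interval exists, selection remains in the pre-treatment slope, which is why the simulated reference is needed.
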